#### *2.14. Assessment of health-related quality of life and patients' preferences*

Health-related quality of life will be elicited using the SF36 and the EQ-5D-5L. It can be expected that adherence to life style and dietary recommendations are associated with risk and time preferences. Hence, risk and time preferences will be elicited based on lottery approaches. Regarding risk preferences, participants will be asked to choose between two hypothetical lotteries that differ in expected outcomes which enables us to derive an individual classification of the risk type, i.e. risk-averse, risk-neutral or risk-loving. Time preferences will be elicited in a similar lottery framework whereat participants are faced with a trade-off between lower benefits now or higher benefits later on. Time preferences allow us to classify participants according to present-biased individuals and patient ones. Quality of life as well as risk and time preferences will be assessed at V1, VPP1, and VPP2. Obstetrical patient's satisfaction will be additionally assessed at VPP1 by using the Wijma score.

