
Unfortunately, both randomized controlled studies used older versions of a blinded CGM device, where glucose values are not directly visible for patients. In contrast, more recently developed "real-time" CGM (rt-CGM) systems provide users with information about current glucose levels and alert the patient before the upper or lower glucose threshold is reached or when glucose levels change rapidly. Hence, glycaemic excursions can be rapidly identified and accordingly adapted by behavioural change or pharmacologic intervention. A number of studies including non-pregnant patients have shown superiority of rt-CGM over

older blinded CGM versions in order to effectively empower and educate patients with diabetes to better understand how dietary habits, exercise or pharmacotherapy affects their glucose levels. A beneficial effect of rt-CGM in pregnancy was also supported by the CONCEPTT trial for pregnant women with type 1 diabetes. Only one recent study compared SMBG with rt-CGM in women with GDM using a single application for 3–7 days within two weeks after diagnosis but it failed to demonstrate improvements in HbA1c or pregnancy outcomes, which was, however, likely due to the sample size and the short duration of intervention (single application).

Taken together, larger randomized controlled studies adequately powered to evaluate the impact of long-term application of rt-CGM systems on the risk reduction of adverse obstetric outcomes are missing. Of note, such studies are of high clinical relevance because of their guideline-changing potential. In addition, rt-CGM has the potential to reduce reported barriers to SMBG (such as inconvenience, pain or stigma of testing in public places) in order to improve poor reliability and adherence to glucose monitoring, which is a non-negligible problem in the treatment of GDM.

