## *2.2. Study visits pregnancy*

A broad risk evaluation will be performed in participating females at the initial contact (V1) including: evaluation of maternal age, parity, history of GDM in previous pregnancies, detailed family history, ethnicity, preconceptional diseases, obstetric history. Height (stadiometer measured to the nearest centimeter) and actual weight (calibrated scales, no clothes) will be additionally assessed. Moreover, an evaluation of preconceptional weight (self-reported) and BMI as well as measurement of blood pressure will be performed. All patients receive medical nutrition therapy (isocaloric diet containing 40-50% carbohydrates, 20% proteins and 30-35% fat, divided into three meals and three snacks) and lifestyle advice for 30 minutes following international recommendations and are advised on capillary blood glucose measurement (fasting as well as 1h after starting each meal) at the initial visit (V1). Randomisation will be done after a run-in period of 6 to 8 days (V2). The run-in period is omitted for patients who had a diagnosis of GDM before 24+0 according to the local guidelines and already received medical nutrition therapy, lifestyle intervention and advices on capillary blood glucose measurements. The third visit (V3) will be scheduled 8 to 10 days after V2 and further follow-up visits every two weeks (i.e. 12 to 16 days after each visit). HbA1c and glycosylated fibronectin, hsCRP, proBNP, Troponin T, will be assessed at V2 as well as at the first visit between 36+0 and 38+6 weeks of gestation (12 ml, non-fasting state) (V4). Detailed fetal ultrasound examinations, a detailed examination of dietary intake as well as a blinded CGM (control group only) will be performed at V2 and V4. Body weight change and use of glucose lowering medications (amount of insulin units) will be examined at every visit. At every follow-up visit glucose measurements (SMBG or rt-CGM) and routine ultrasound examinations (fetal biometry and umbilical artery doppler) will be evaluated by the medical staff and all patients will be treated according to the standard of care for patients with GDM. This includes lifestyle modification and insulin therapy if recommended thresholds are exceeded. Both groups will be treated to be in the target range between 65 to 140 mg/dl [3.6 to 7.8 mmol/l] with at least 8h fasting glucose levels equal or below 95 mg/dl [5.3 mmol/l] and 1h postprandial glucose

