### *2.3 Study visits postpartum*

Cord blood will be sampled and stored (at  $-80^{\circ}\text{C}$ ) immediately after delivery (VPP0). A postpartum examination will be scheduled within 48 hours after delivery (VPP1) for assessment of neonatal parameters and maternal HbA1c and glycosylated fibronectin, hsCRP, proBNP, Troponin T, (12 ml, non-fasting state), as well as between **8 weeks and 12 months** after delivery (VPP2) in all patients for a detailed re-examination of glucose homeostasis at postpartum (including lifestyle and dietary pattern as well as HbA1c, glycosylated Fibronectin, hsCRP, proBNP, Troponin T, as well as a blinded CGM for 10 days and an OGTT to assess the presence of prediabetic conditions after pregnancy with GDM). The postpartum OGTT is further used to provide estimates of insulin sensitivity,  $\beta$ -cell function and hepatic insulin extraction, the major physiological components of impaired glucose tolerance.

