### *2.4. Randomisation*

Participants will be randomized to either treatment (rt-CGM augmented glucose monitoring) or control group (routine care SMBG) in a 1:1 ratio. The minimisation method with a 0.85 assignment probability will be used to minimize the imbalance between the groups according to week of gestation at study entry i.e. at V1 (three strata: 24+0 to 25+6, 26+0 to 27+6, 28+0 to 29+6, 30+0 to 31+6), previous pregnancy with GDM (two strata: yes or no) and preconceptional overweight/obesity status with three strata: i. normal weight (i.e. BMI below  $25.0 \text{ kg/m}^2$ ); ii. overweight ( $\text{BMI } 25.0 - 29.9 \text{ kg/m}^2$ ); iii. obesity ( $\text{BMI equal or above } 30.0 \text{ kg/m}^2$ ). Randomisation will be performed at the second study visit (V2) by using the "MUW Randomizer" software.

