#### *2.8. Assessment of physical activity*

Physical activity will be assessed at V1, VPP1, and VPP2 via the International IPAQ (Physical Activity Questionnaire, long form). The IPAQ represents a well-accepted, validated instrument for monitoring population levels of physical activity in different settings and countries. It will be analysed via published guidelines for data processing and analysis at the IPAQ homepage Guidelines for data processing and analysis of the international physical activity questionnaire (IPAQ): In short, collected data will be summarized as median MET (metabolic equivalent of task) minutes per week, representing a continuous score for walking, moderate intensity activities, vigorous intensity activities and total activities, as recommended. In addition, the Pregnancy Physical Activity Questionnaire (PPAQ) will be performed to capture information on physical activity participation and sedentary behaviour during pregnancy.

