#### *2.15. Health economic evaluation*

For the evaluation of a complex intervention, a health economic evaluation is recommended as well. In this study, a cost-effectiveness and a cost-utility analysis will be performed from the perspective of the health insurance. Effect measures will be avoided cases of LGA newborns as well as quality-adjusted life-years (QALYs). QALYs will be calculated using the SF36 assessment and the SF-6D that derives preference-based scores from the SF-36 by using population-based preferences (utilities) for the SF-36 health states. Intervention costs as well as health care costs (direct costs) will be calculated. For the elicitation of health care use a validated instrument will be used. Health care use will include e.g. clinical visits for the mother and associated procedures during trial and after delivery, inpatient stays, office-based visits, medication, glucose monitoring supplies and devices. Costs will be estimated and considered from the perspective of the health insurance. Since the evaluation covers only the observation period alongside the trial, costs and effects will not be discounted. Outcomes are incremental cost-effectiveness and cost-utility ratios (ICER/IUCR: additional cost per additional LGA newborn avoided or per quality-adjusted life year gained).

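### Quality of life is never measured while the two monitoring methods are in use, so an HRQoL or QALY difference confined to pregnancy may be partly or wholly missed

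*Combined protocol and SAP*

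**What the plan says.** Section 2.14 names the instruments: "Health-related quality of life will be elicited using the SF36 and the EQ-5D-5L". It then fixes the times: "Quality of life as well as risk and time preferences will be assessed at V1, VPP1, and VPP2". Section 2.2 places allocation after the run-in: "Randomisation will be done after a run-in period of 6 to 8 days (V2". Section 2.4 agrees: "Randomisation will be performed at the second study visit (V2". The intervention part of section 2.5 has the rt-CGM sensor fitted at that same visit. Section 2.3 times the first postpartum visit: "A postpartum examination will be scheduled within 48 hours after delivery (VPP1". It places VPP2 between 8 weeks and 12 months after delivery, when both arms wear a blinded sensor.

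For the economic evaluation, section 2.15 says: "QALYs will be calculated using the SF36 assessment and the SF-6D". It counts monitoring devices and consumables among the costs and limits the horizon to the trial's observation period. Section 1.3 lists HRQoL with the secondary objectives. Sections 2.14, 2.15 and 3.2 give no recall period for the forms, no visit for the HRQoL comparison, and no rule for joining utilities between visits.

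**The concern.** The arms differ in monitoring method from V2 until about delivery. One HRQoL assessment lies before that period and two lie after it. The only post-randomisation value near treatment is given within two days of labour or caesarean section, so it mixes any effect of monitoring with the effects of the birth.

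Two objectives are exposed. The HRQoL comparison has no direct on-treatment observation. The cost-utility ratio charges the devices to a period in which utility is inferred rather than observed. If both come out null, the trial could not say whether rt-CGM made no difference to women during use or whether the difference was simply not observed.

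**Working it through.** The documents give no HRQoL or QALY figure to reproduce, so the check starts with the schedule.

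| Visit | Timing | Allocated monitoring | SF-36, EQ-5D-5L |
|---|---|---|---|
| V1 | after diagnosis, up to 31+6 weeks | not yet allocated | yes |
| V2 | 6 to 8 days after V1 | allocation, sensor fitted | no |
| V3 | 8 to 10 days after V2 | in use | no |
| Follow-up | every two weeks | in use | no |
| V4 | 36+0 to 38+6 weeks | in use | no |
| VPP1 | within 48 h after delivery | pregnancy over | yes |
| VPP2 | 8 weeks to 12 months after delivery | same blinded CGM in both arms | yes |

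HRQoL assessments between V2 and delivery: 0. Section 2.2 omits the run-in for some women diagnosed before 24+0. That brings V1 close to V2 but adds no later assessment. Section 2.13 gives 8 to 16 weeks for the OGTT at VPP2, which is also after the treatment period.

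**Assumptions, not in the documents:** V1 at 24+0 to 31+6, a 7-day run-in, delivery at 37 to 40 weeks, no arm difference at V1, a constant utility difference d = 0.03 from V2 to delivery and none after it, and linear interpolation between assessments. The shares below do not depend on d.

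**Unobserved window, L = delivery − V2**
- Shortest: V1 at 31+6, so V2 at 32+6, delivery at 37 weeks: L = 4.1 weeks.
- Longest: V1 at 24+0, so V2 at 25+0, delivery at 40 weeks: L = 15 weeks.
- Central: V1 at 28+0, so V2 at 29+0, delivery at 39 weeks: L = 10 weeks.

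**True pregnancy gain = d × L/52**
- Central: 0.03 × 10/52 = 0.0058 QALY. Range: 0.03 × 4.1/52 = 0.0024 to 0.03 × 15/52 = 0.0087.

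**Credited by the planned schedule = 0.5 × (difference at VPP1) × G/52, where G = delivery − V1 (central: 11 weeks)**
- Arms equal at VPP1: 0, or 0% of the gain.
- Full difference still recorded at VPP1: 0.5 × 0.03 × 11/52 = 0.0032, or 55% of the gain (53 to 62% across the scenarios). The same value is then carried forward towards VPP2. This adds 0.5 × 0.03 × 8/52 = 0.0023 if VPP2 is at 8 weeks, or 0.5 × 0.03 × 52/52 = 0.0150 if it is at 12 months. The total is 0.0055 to 0.0182 against a true 0.0058.

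The planned schedule can therefore credit none of the gain, about the right amount, or about three times too much. Which of these happens depends on the answer given just after birth and on the timing of VPP2.

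**With on-treatment assessments added (delivery at 39 weeks, arms equal at VPP1)**
- V4 added: 0.5 × 0.03 × 11/52 = 0.0032, or 55% (54 to 58% over the range of V1).
- V3 and V4 added, V3 at 29 + 9/7 = 30.286 weeks and V4 at 37: weeks credited = 0.5 × 2.286 + 6.714 + 0.5 × 2 = 8.857 of 10, or 89% (81 to 92%).

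**The case against.** The strongest reply is that the loss is not certain. A form that asks about past weeks, or a difference that persists at VPP1, would recover part of the pregnancy effect. The documents state neither a recall period nor an interpolation rule, and they give no date on which the sensor comes off. This stands: the schedule does not measure the effect directly, but it cannot be said that no effect could ever show. Even a form with recall would be answered within 48 hours of birth.

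Four stronger readings are tempting, and the documents do not carry them.

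- A reader might infer that the protocol itself predicts better quality of life in pregnancy, because section 1.1 says "rt-CGM has the potential to reduce reported barriers to SMBG (such as inconvenience, pain or stigma of testing in public places". That sentence goes on to link fewer barriers to reliability and adherence. Section 1.2 states no HRQoL hypothesis. A benefit during use is a reasonable inference from section 1.1, not a claim of the plan.
- A reader might infer that the dip in utility after birth creates an error as large as the effect sought. An incremental QALY is a difference between arms, so a dip common to both cancels. Assume a caesarean-related dip of 0.05 to 0.10, a 10-percentage-point difference in caesarean rate, and 8 to 14 weeks of interpolation. The residual is then 0.10 × 0.5 × 0.05 × 8/52 = 0.0004 to 0.10 × 0.5 × 0.10 × 14/52 = 0.0013 QALY. Part of that could be a real treatment effect.
- A reader might infer the same gap for exercise, since section 2.8 says "Physical activity will be assessed at V1, VPP1, and VPP2 via the International IPAQ". That section also adds the PPAQ specifically for activity in pregnancy, without naming a visit.
- A reader might infer that the error always works against rt-CGM. The working shows that it can go either way.

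**Conclusion.** The point holds as a gap in the measurement schedule. HRQoL has no direct observation during randomised monitoring, and the cost-utility analysis inherits that gap while counting device costs in the same period. The schedule finding rests on the documents alone. The QALY amounts rest on the assumptions listed in the working. With d = 0.03, a pregnancy gain of 0.0024 to 0.0087 QALY is credited at 0% if the arms are equal at VPP1, and is misallocated in time if they are not. A null HRQoL or QALY result could not be read as no benefit during use. The primary outcome and the cost per LGA newborn avoided are not affected, so this is a worthwhile and cheap improvement rather than a threat to the trial's main conclusion.

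**What to change.** - In section 2.14, add the SF-36 and EQ-5D-5L at V4 (36+0 to 38+6), which both arms already attend, and name V4 as the visit for the on-treatment HRQoL comparison. Women who deliver before V4 complete the set at their last antenatal visit where possible.
- Keep VPP1 and VPP2. Replacing VPP1 by V4 would join V4 directly to VPP2. With V1 at 28 weeks, V4 at 37, delivery at 39 and VPP2 at 12 months, that credits 0.5 × 0.03 × (9 + 54)/52 = 0.018 QALY against a true 0.0058.
- In sections 2.15 and 3.2, state that the QALY curve is built from V1, V4, VPP1 and VPP2, give the interpolation rule, and state the recall period of the forms.
- V3 could be added as well if burden allows. Under linear interpolation it raises the share recovered from 54–58% to 81–92%.

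The cost is protocol wording and one more questionnaire set at an existing visit. Women already past V4 will have no value there. If the schedule cannot change, restrict the HRQoL and QALY conclusions to the peripartum and postpartum period.

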#### *2.15. Health economic evaluation*

For the evaluation of a complex intervention, a health economic evaluation is recommended as well. In this study, a cost-effectiveness and a cost-utility analysis will be performed from the perspective of the health insurance. Effect measures will be avoided cases of LGA newborns as well as quality-adjusted life-years (QALYs). QALYs will be calculated using the SF36 assessment and the SF-6D that derives preference-based scores from the SF-36 by using population-based preferences (utilities) for the SF-36 health states. Intervention costs as well as health care costs (direct costs) will be calculated. For the elicitation of health care use a validated instrument will be used. Health care use will include e.g. clinical visits for the mother and associated procedures during trial and after delivery, inpatient stays, office-based visits, medication, glucose monitoring supplies and devices. Costs will be estimated and considered from the perspective of the health insurance. Since the evaluation covers only the observation period alongside the trial, costs and effects will not be discounted. Outcomes are incremental cost-effectiveness and cost-utility ratios (ICER/IUCR: additional cost per additional LGA newborn avoided or per quality-adjusted life year gained).

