## 2. Research Design and Methods

### 2.1. Participants and recruitment; Exclusion criteria

This study is designed as an open-label multicentre randomized controlled trial with two parallel groups including a total of 372 female patients (n=186 with rt-CGM, n=186 with SMBG) with recent diagnosis of GDM. Diagnosis of GDM (i.e. diabetes first diagnosed in second and third trimester and not clearly type 1 or type 2 diabetes) is made in accordance with the IADPSG criteria after 24+0 weeks of gestation by a 2h 75g OGTT. If the GDM diagnosis is made before 24+0 weeks of gestation in accordance with the local guideline (i.e. when IADPSG cut-offs for fasting and post-load glucose are exceeded) patients can be included if no insulin treatment was started until 24+0^21. The study will be conducted at four tertiary referral centres in Austria, Switzerland, Sweden and Germany. All pregnant females (aged between 18 and 55 years) will be consecutively recruited after diagnosis of GDM until 31+6 weeks of gestation among women visiting the pregnancy outpatient departments (Division of Obstetrics and feto-maternal Medicine, Medical University of Vienna; Division of Obstetrics, University Hospital Basel, Clinic of Obstetrics, Charité Berlin, Clinic of Obstetrics, University Hospital Jena) or the diabetes outpatient departments (Division of Endocrinology and Metabolic Diseases at the Heinrich Heine University, Düsseldorf; Department of Medicine, University Hospital, Örebro).

Exclusion criteria are:

Overt diabetes (i.e. pregestationally known type 1 or type 2 diabetes or fasting plasma glucose during the OGTT  $\geq 126$  mg/dl [7.0 mmol/l] or HbA1c  $\geq 6.5\%$  [44 mmol/l] or 2h post-load OGTT levels  $\geq 200$  mg/dl [11.1 mmol/l] assessed before 24+0 weeks of gestation, whereby results need to be confirmed by repeated testing in case of unequivocal hyperglycemia according to the ADA standards); History of bariatric surgery or other surgeries that induce malabsorption; Long-term use (>2 weeks) of systemic steroids prior to enrolment; Multiple pregnancy; Patients already using glucose lowering medications (metformin or insulin) before study entry; fetal growth restriction due to placental dysfunction at study entry; Inpatient psychiatric treatment up to 1 year before enrolment; Participation in this study in previous pregnancy;

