newborn avoided or per quality-adjusted life year gained) will be calculated. 95% confidence intervals will be analysed using bootstrap procedures. To consider uncertainty, univariate and probabilistic sensitivity analyses will be performed and cost-acceptability curves will be created. A two-sided p-value  $\leq 0.05$  is considered statistically significant. All analyses will be performed by using the statistic software R and contributing packages. No further adjustment for multiplicity is planned for this study.

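### No adjustment of the QALY difference for SF-6D utility at V1 is specified, and the precision that adjustment would gain depends on a QALY horizon the plan does not set.

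*Combined protocol and SAP*

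**What the plan says.** All places are in the combined protocol and SAP.

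- **Source of QALYs.** Section 2.15: "QALYs will be calculated using the SF36 assessment and the SF-6D". It gives no rule for turning the utilities into a QALY and no horizon beyond the observation period of the trial.
- **Timing of utilities.** Section 2.14: "Quality of life as well as risk and time preferences will be assessed at V1, VPP1, and VPP2".
- **Timing of randomisation.** Section 2.4: "Randomisation will be performed at the second study visit (V2"). Section 2.2 puts a run-in of 6 to 8 days between V1 and V2, omitted for some women diagnosed before 24+0 weeks.
- **Balance by design.** Minimisation uses gestational week at entry, plus "previous pregnancy with GDM (two strata: yes or no) and preconceptional overweight/obesity status with three strata". Utility is not a factor.
- **Economic analysis.** Section 3.2 lists incremental ratios, univariate and probabilistic sensitivity analyses and acceptability curves, and says "95% confidence intervals will be analysed using bootstrap procedures". No covariate is named. The only adjusted arm comparison in that section is a Cochran-Mantel-Haenszel sensitivity analysis for centre.
- **VPP2 window.** The synopsis and section 2.3 give 8 weeks to 12 months after delivery; section 2.13 gives 8 to 16 weeks.

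**The concern.** V1 utility is measured before allocation, so a difference between arms at V1 cannot be caused by rt-CGM. It can reach the QALY difference in two ways: as a term in each woman's QALY, and through its correlation with her utilities at VPP1 and VPP2. If the difference is not adjusted, a chance imbalance at V1 is reported as QALYs gained or lost. The bootstrap interval allows for that chance variation but does not move the estimate back.

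At stake is the precision of the incremental QALY, and with it the cost-utility ratio, its interval and the acceptability curve. The QALY is the denominator of that ratio and is likely to be small, so modest shifts matter. Leaving the choice open also means that, in an open-label trial, adjustment could be decided after the data are seen.

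**Working it through.** **The plan's own figure.** There is none for the QALY comparison. The LGA sample size reproduces: 13.7% against 25.8%, two-sided 0.05, 80% power gives 169 per group, and 338 × 1.1 = 371.8, stated as 372. It is used here only for the number of women: 186 × 0.9 = 167.4, so 167 per arm. Using 169 instead changes a standard error by under 1%.

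**Assumptions, not in the documents.** SF-6D SD 0.10 at each visit; the same correlation r (0.4 or 0.6) between any two visits; T1 = 12 weeks from V1 to VPP1; T2 = 8 or 52 weeks from VPP1 to VPP2, the ends of the wider window; area under straight lines between visits.

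**Step 1: one horizon for all women.**

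QALY = a·U(V1) + b·U(VPP1) + c·U(VPP2), with a = T1/(2×52), b = (T1+T2)/(2×52), c = T2/(2×52).

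- T2 = 8: a = 0.115, b = 0.192, c = 0.077; V1 carries 6/20 = 30% of the weight.
- T2 = 52: a = 0.115, b = 0.615, c = 0.500; V1 carries 6/64 = 9%.

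Variance = 0.10² × [a² + b² + c² + 2r(ab + ac + bc)]. Slope on V1 utility = a + r(b + c). R² = slope² × 0.10² / variance. Unadjusted SE = √(2 × variance/167); adjusted SE = unadjusted SE × √(1 − R²).

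| T2 (weeks) | r | Slope | R² | SE unadjusted | SE adjusted | Reduction |
|---|---|---|---|---|---|---|
| 8 | 0.4 | 0.223 | 0.54 | 0.0033 | 0.0023 | 32% |
| 8 | 0.6 | 0.277 | 0.69 | 0.0037 | 0.0020 | 44% |
| 52 | 0.4 | 0.562 | 0.32 | 0.0109 | 0.0090 | 17% |
| 52 | 0.6 | 0.785 | 0.53 | 0.0118 | 0.0081 | 31% |

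Wider assumptions (SD 0.10 to 0.15, r 0.3 to 0.7, V1 at 24 to 31+6 weeks, delivery at 39.5 weeks, 169 per arm) put the adjusted SE at 0.47 to 0.90 of the unadjusted one.

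**Step 2: chance imbalance at V1.** The 95% limit is 1.96 × 0.10 × √(2/167) = 0.0214. Multiplied by the slope, it moves the unadjusted QALY difference by 0.0048 to 0.0059 (T2 = 8) or 0.0120 to 0.0168 (T2 = 52). The V1 term alone gives 0.115 × 0.0214 = 0.0025; the rest comes through correlation with later utilities.

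For scale on the same horizons, a true gain of 0.02 present at both VPP1 and VPP2 is worth 0.02 × (b + c) = 0.0054 QALY (T2 = 8) or 0.0223 QALY (T2 = 52).

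**Step 3: QALYs accrued to each woman's own VPP2.** Differing follow-up adds variance that V1 utility does not explain. Assume mean utility 0.7 and T2 uniform over the window. Total variance = mean of the Step 1 variance over T2 + (0.7/52)² × (window width)²/12.

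- Window 8 to 52 weeks: the added term is (0.7/52)² × 44²/12 = 0.0292, against 0.0046 (r = 0.4) or 0.0054 (r = 0.6) from the utilities. The mean slope is 0.392 or 0.531, so R² is 0.05 or 0.08, and the SE reduction is 2% or 4%.
- Window 8 to 16 weeks: the added term is (0.7/52)² × 8²/12 = 0.00097, against 0.0013 or 0.0016. The mean slope is 0.254 or 0.323, so R² is 0.28 or 0.40, and the reduction is 15% or 23%.

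**The case against.** **The plan is silent; it does not choose an unadjusted comparison.** Section 3.2 calls itself a selection of methods, and an adjusted increment could be bootstrapped within its wording. This stands. A reader might infer that raw arm totals will be compared, but no section says so. What the documents support is that adjustment is not specified.

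**The QALY rule is inferred.** This also stands. That V1 enters the QALY is very likely, because no other utility covers the pregnancy, but it is not written. Every figure above rests on the area-under-the-curve assumption. If V1 were left out of the QALY, it would still predict the later utilities.

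**Randomisation already protects the comparison.** It does so on average. A reader might infer systematic bias or an invalid interval; neither follows. A shift of the size in Step 2 is an event at the edge of the 95% chance range, and the unadjusted bootstrap interval includes that variation. The loss is one of efficiency.

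**Chance imbalance need not swamp the effect.** It is tempting to set the 0.0168 shift against 0.02 utility held for 12 weeks, 0.02 × 12/52 = 0.0046 QALY. That compares a 64-week horizon with a 12-week one. On matched horizons the shift is about the size of the illustrative gain when T2 is 8 weeks and below it when T2 is 52 weeks. The plan states no economic decision threshold, so no reversed conclusion is shown.

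**The gain may be slight.** With individual horizons over the wider window it nearly disappears. This is a reason to fix the horizon together with the adjustment.

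**Conclusion.** The point holds as a gap in specification. Sections 2.15 and 3.2 name no adjustment for a pre-randomisation utility that is already collected, very likely forms part of each QALY and predicts the rest. The unadjusted difference is unbiased on average but less precise, and it passes any chance V1 imbalance on to the cost-utility ratio.

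The size depends on the horizon: a 17% to 44% smaller SE with one common horizon, 15% to 23% if QALYs run to individual VPP2 dates over 8 to 16 weeks, and 2% to 4% over 8 to 52 weeks. The SD, correlations, mean utility, visit spacing and spread of VPP2 dates are assumptions. Adjustment without a common horizon could therefore achieve very little.

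Only the secondary cost-utility analysis is affected. The LGA test and the cost per LGA newborn avoided are not.

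**What to change.** **Section 2.15.** State that each woman's QALY is the area under her SF-6D utilities at V1, VPP1 and VPP2 over one horizon common to all women, and how utility is taken to that horizon when VPP2 falls before or after it. Reconcile the VPP2 window in the synopsis and section 2.3 with the one in section 2.13.

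**Section 3.2.** Suggested text: *The QALY difference is estimated by regressing QALY on arm and V1 SF-6D utility. The regression is refitted in every bootstrap resample. The adjusted difference is used for the cost-utility ratio, its confidence interval and the acceptability curve. The unadjusted difference is shown as a sensitivity analysis.*

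For women whose run-in is omitted, it is worth confirming that the SF-36 is completed before allocation is known, so that V1 remains a baseline value for everyone.

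**Cost.** A few sentences in the plan and one regression inside the bootstrap code. No new data, visits or participants are needed, since the V1 SF-36 is already scheduled. Choosing the horizon and reconciling the VPP2 window are the only parts that need discussion.
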